## IX. RESEARCH DESIGN AND METHODS

### Design

We will use a prospective, randomized, experimental design to accomplish the specific aims. Subjects (n=345) will be randomly assigned within 36 hours of intubation to one of three intervention groups which differ in frequency of tooth brushing (once, twice, or three times daily). The intervention, a standardized tooth brushing protocol developed and tested in the previous project, will be delivered by study personnel. Subjects will continue to receive scheduled interventions for the first 7 days of intubation, or until extubated if extubation occurs within 7 days; for subjects extubated within the intervention period, data collection will continue on days 1, 3, and 5 post-extubation. Dental plaque assessment, GCF for IL-1 $\beta$  determination, and data regarding HAIs and clinical status (for example, severity of illness) will be collected daily by study personnel who are blinded to group assignment.

All subjects will receive standard clinical care for mechanically ventilated patients, as per clinical guidelines and clinical agency guidelines. Standard clinical care includes all components of the IHI ventilator care bundle, including daily CHX. All subjects will receive oral comfort care by clinical providers at the provider's discretion. We will monitor reported compliance with the ventilator care bundle, and record characteristics and frequency of oral comfort care provided in order to assure that groups do not differ in usual clinical care.

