
Once the subject has been enrolled, the Project Director will assign the subject to one of the three groups using a randomization schedule generated by [name]. A set of sequenced, sealed opaque envelopes will be prepared, each containing the assignment of an individual subject. At the time of enrollment, the Project Director will open the next envelope and proceed accordingly. [name] and the Data Manager will each keep a master copy of the randomization assignment.

Intervention and data collection procedures. Following obtainment of informed consent from the subject or LAR, subjects will be randomly assigned within 36 hours of intubation to one of three intervention groups which differ in frequency of tooth brushing (once, twice, or three times daily). The intervention, a standardized tooth brushing protocol developed and tested in the previous project, will be delivered by study personnel for 7 days, or until the subject is extubated if extubation occurs within the first 7 days.

Daily saliva periopaper GCF samples will be collected and digital images of teeth will be taken and identified only by the subject's arbitrary study number, not by any identifiable private information. GCF samples will be frozen at  $-70$  degrees in the Tampa General Hospital Office of Clinical Research Laboratory, and later transported to the

Biobehavioral Laboratory at the USF CON, and stored securely in the locked, limited access laboratory. Digital images of teeth will be obtained at close range such that photos will not include subject facial features.

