Data will be obtained from the patient's medical record, from assessment of the subject's mouth, and from biologic fluids (gingival crevicular fluid, GCF, collected on filter paper). On study admission, the following data will be collected: demographic data (age, gender, smoking status, reason for admission), severity of illness data (APACHE information), and a count of decayed, missing and filled teeth (DMFT). The following data will be collected every day through the first seven days of mechanical ventilation, or until extubated if extubation occurs within the first seven days: digital photos of all teeth (for use in UM-OHI dental plaque assessment), a sample of GCF collected on Periopaper (for GCF IL-1 $\beta$  assay), Systemic Inflammatory Response Syndrome criteria from the medical record, positive epidemiologic surveillance reports for enrolled subjects for VAE (including VAP), bacteremia, and sepsis from the TGH Epidemiology Department records. For subjects who are extubated during the first 7 days of mechanical ventilation, the same data collected during the study intervention period will also be collected after extubation on days 1,3,5 after extubation. Data regarding length of intubation, length of ICU stay and length of hospital stay will also be calculated from the medical record.

All data, including digital photos, will be collected on laptops in the clinical setting; these laptops will remain in the possession of study personnel at all times (unless locked in a cabinet in the locked research office), and all study-related files will be password protected. At the conclusion of each subject's participation, that subject's data will be transferred from the laptop computer to a secure, password protected file on the USF Health server, under the direct supervision of [name], with access limited to study personnel. Study information obtained will be kept strictly confidential, and it will not be possible to identify any participant from the reports that may result from this research.

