Specific Aim 2 is to quantify and compare the safety of three tooth brushing frequencies on serious adverse outcomes, including ventilator associated complications and clinically relevant healthcare-associated infections. For aim #2, a composite HAI endpoint will be constructed consisting of VAP, bacteremia, and sepsis. Since HAIs are anticipated to be rare events across the 3 tooth brushing regimens, no formal between-group statistical testing will be conducted. Instead, 95% confidence intervals will be calculated for the proportion of subjects with HAI in each treatment arm. In addition, using person days of observation (i.e. days since intubation), we will calculate incidence rates (IR) of HAI by treatment arm and then calculate the number needed to harm (NNH) using the single daily brushing regimen as the

reference group and the formulas:  $NNH_{21} = (1 / (IR_2 - IR_1))$  and  $NNH_{31} = (1 / (IR_3 - IR_1))$  where  $IR_n$  = observed incidence rate in each treatment arm. In the event that the formal test of non-inferiority fails for the single daily brushing regimen, we will define clinically-relevant “compromised” safety as an NNH of 100 per less. This would be interpreted as 100 individuals or less being treated with the multiple daily tooth brushing to develop an HAI that otherwise would not have occurred with the single daily brushing regimen.

Clinical recommendations defined *a priori* and developed from the analyses conducted for aims 1 and 2 will be developed as defined in Table 2.

Table 2. Application of study findings to tooth brushing frequency recommendations

Comparison Groups a	Non-Inferiority	NNH	Recommendation	Rationale
1 versus 3	Supported	N/A	1 time/day	1 time/day non-inferior and safe
1 versus 3	Not supported	$\geq 100$	3 times/day	1 time/day inferior, 3 times/day safe
1 versus 3	Not supported	$< 50$	1 time/day	1 time/day inferior, but 3 times/day safety concern
1 versus 3	Not supported	50 to 100	See 1 vs. 2	1 time/day inferior, but 3 times/day safety concern
1 versus 2 b	Supported	N/A	1 time/day	1 time/day non-inferior and safe
1 versus 2 b	Not supported	$\geq 100$	2 times/day	1 time/day inferior, 2 times/day safe
1 versus 2 b	Not supported	$< 100$	1 times/day	1 time/day inferior, but 2 times/day safety concern

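### Person-time for the HAI rate does not stop at extubation, so days without study brushing can dilute the rate differences and inflate the NNH that Table 2 acts on

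*Combined protocol and SAP*

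**What the plan says.** Section XI, Specific Aim 2, defines the endpoint: "a composite HAI endpoint will be constructed consisting of VAP, bacteremia, and sepsis". For the rates, "using person days of observation (i.e. days since intubation), we will calculate incidence rates (IR) of HAI by treatment arm". The NNH is the reciprocal of a rate difference, with once daily as reference: NNH31 = 1/(IR3 − IR1) and NNH21 = 1/(IR2 − IR1). The cut-off is read in persons: "This would be interpreted as 100 individuals or less being treated with the multiple daily tooth brushing to develop an HAI". When non-inferiority of once daily against three times daily is not supported, Table 2 applies limits of 50 and 100 to NNH31. At 100 or more it labels three times daily safe.

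Exposure ends earlier than observation. Section IX, Design: "Subjects will continue to receive scheduled interventions for the first 7 days of intubation, or until extubated if extubation occurs within 7 days". Section IX, Procedures, covers those extubated in the first 7 days: "the same data collected during the study intervention period will also be collected after extubation on days 1,3,5 after extubation". The data in question include surveillance reports of VAE, bacteremia and sepsis. The footnote to Table 1 adds that subjects still intubated after the 7-day period have no post-extubation collection.

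**The concern.** On its plain wording the denominator runs from intubation to the end of observation. For anyone extubated within 7 days it therefore joins time under the randomised brushing frequency to as many as 5 days in which no arm receives study brushing. Background and Significance and Section XVI.E (Potential Risks) both describe the harm as organisms dislodged in the act of brushing and then aspirated or carried into the blood. Under that mechanism the difference between arms should be concentrated in the brushing period and a short time after it.

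Adding days with little or no excess pulls IR3 − IR1 and IR2 − IR1 towards zero and raises both NNHs. Table 2 reads a larger NNH as reassurance about more frequent brushing, so the dilution acts on the recommendation itself. It is also uneven. Early-extubated subjects are diluted most and those intubated past day 7 not at all, so each arm's rate depends on its mix of extubation days.

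**Working it through.** **The plan's own figures.** The only computed Aim 2 figure is the 95% interval for an HAI proportion of 0.05 with n = 69. An exact binomial interval with 0.05 × 69 = 3.45 events gives 0.012 to 0.131, which matches the stated 0.01 to 0.13. The plan gives no expected rate or NNH, so there is none to reproduce.

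**One subject.** Extubated on day d and followed 5 more days, the intubated share of person-time is d/(d + 5): 0.29 at d = 2, 0.44 at d = 4, 0.58 at d = 7.

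**A group.** Inputs from the plan: brushing to day 7 or extubation; 5 post-extubation days only if extubated within 7 days; up to 40% of subjects not analysable (Section XI, Statistical Power). That 40% also covers missing data, so I use it as an upper value for extubation before 48 hours and take 20% as a lower one. My assumptions: exponential time to extubation T; 7 counted days for those intubated beyond day 7; all 5 days completed by the others; the same extubation pattern in both arms.

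- Hazard λ = −ln(1 − p)/2, where p is the proportion extubated before 48 hours.
- Proportion extubated within 7 days: q = 1 − exp(−7λ).
- Mean intubated days V = q/λ; mean post-extubation days P = 5q.
- If the full excess rate persists for L days after extubation and is then zero, NNH inflation = (V + P)/(V + Lq).

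| p | q | V | P | L = 0 | L = 1 | L = 2 |
|---|---|---|---|---|---|---|
| 0.20 | 0.542 | 4.86 | 2.71 | 1.56 | 1.40 | 1.27 |
| 0.40 | 0.833 | 3.26 | 4.16 | 2.28 | 1.81 | 1.51 |

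For example, at p = 0.40 and L = 2: 7.42/(3.26 + 1.67) = 1.51.

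**Dependence on direction.** If the post-extubation excess rate is r times the intubated excess rate throughout, inflation = (V + P)/(V + rP). At p = 0.40 this is 1.73 for r = 0.25, 1.39 for r = 0.5, 1.00 for r = 1 and 0.78 for r = 1.5. So there is no inflation at equality, and the NNH falls if the excess is higher after extubation.

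**Effect on Table 2.** With a 2-day carry-over, an NNH of 45 on the exposed window is reported as 57 to 68 (45 × 1.27 to 45 × 1.51). That moves it from the row below 50 to the row from 50 to 100. An NNH of 80 becomes 102 to 121 and moves into the row of 100 or more.

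**Units.** Suppose 5% versus 10% HAI and a mean of 4 intubated days. The NNH in individuals is 1/0.05 = 20. From intubated-day rates it is 4/0.05 = 80. If every subject adds 5 days with no excess, it is 9/0.05 = 180. Restricting the window takes 180 to 80, not to 20.

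**The case against.** Several points on the other side stand, and they limit the claim.

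- The wording could be meant as days intubated. If so, there is no dilution, but the text does not say it and observation plainly continues. Two analysts could obtain different NNHs from the same data, so the wording needs repair either way.
- The added days are not free of risk. Bacteremia and sepsis are in the composite, HAI reports are collected after extubation, and the Preliminary Studies section (study 6) presents post-extubation follow-up as a deliberate feature. Inflation is therefore conditional on a lower excess rate after brushing stops.
- A reader might infer that VAP cannot begin after extubation. The documents do not say so, and the point does not need it.
- A reader might infer that infections on post-extubation days 2 and 4 are missed because no collection is scheduled. Under Serious Outcomes in Section IX, HAIs come from hospital surveillance and the medical record, which can show events on those days.
- A reader might take the largest factor at face value: an NNH of 45 reported as 103 (45 × 2.28), jumping from the lowest row to the safe row. That needs 40% extubated before 48 hours, no carry-over at all and complete 5-day follow-up. The documents do not establish these conditions.
- A brushing-period rate also depends on duration of intubation, which is itself an Aim 2 outcome in Table 1. An arm that prolongs ventilation gains denominator days. This is a real limit of the fix and the reason to keep the proportion beside it.
- The mismatch between person-days and individuals is the larger distortion and would survive this change. It is a separate defect: the window must be defined whichever unit is chosen.

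**Conclusion.** The concern holds in conditional form. The plan does not end person-time at extubation. On its plain wording, up to 5 days without study brushing enter the denominator for subjects extubated within 7 days, and none for those intubated longer. If the excess HAI rate is lower after brushing stops, the NNH is inflated by about 1.3 to 1.5 times with a 2-day carry-over and 1.6 to 2.3 times with none. That is enough to cross a Table 2 cut-off from some starting values.

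These sizes rest on constant-hazard extubation with 20% to 40% out before 48 hours, full post-extubation follow-up and the same extubation pattern in each arm. None of these is given in the documents. If time to extubation differs by arm, the error could go either way. It would be too strong to say that the NNH is certainly inflated.

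**What to change.** In Section XI, Specific Aim 2, replace the parenthetical gloss on person-days, for the rates that feed the NNH, with one prespecified window: the study brushing period plus a fixed lag after it. Apply that window to both events and person-days. The investigators should choose the lag and write it down before the data are seen. The 2 days used above is only an illustration.

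Report HAIs after the window separately by arm. Keep the planned all-follow-up proportion with HAI as the companion comparison: its denominator is subjects, so it does not depend on duration of intubation.

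Separately, reconcile the NNH from per-day rates with cut-offs read as individuals. Either derive the NNH from a risk difference over a fixed horizon, or state both the NNH and its cut-offs in person-days.

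The cost is wording and a little extra analysis. Length of intubation and HAI records are already collected. The drawbacks are fewer person-days and events in the NNH rate, a wider interval, a lag that must be fixed in advance, and a rate that still depends on duration of intubation.

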aTimes per day of tooth brushing. bConducted if the 1 versus 3 test of non-inferiority is not supported and  $NNH_{31}$  is between 50 to 100. NNH: number needed to harm.

Specific Aim 3, to investigate patient factors that influence tooth brushing frequency benefit and risk in critically ill adults, is considered exploratory. Repeated measures linear mixed models will be fit treating dental plaque and mucosal inflammation as separate outcome variables (transformed if required), random group assignment as a 3-level ordinal predictor variable, and a range of possible patient-level predictors. Initially, bivariate correlations for potential continuous predictors and analysis of variance (ANOVA) for potential categorical predictors will be conducted to identify potential patient factors independently associated with dental plaque and mucosal inflammation. Interaction terms between tooth brushing frequency (scored 1, 2, or 3) and individual patient factors will be constructed to assess potential effect modification. The mixed models will be fit using the normal distribution, identity link, and specifying an autoregressive correlation structure. For assessment of safety, and assuming a sufficient number of HAs for model conversion, generalized estimating equations will be fit in the same manner as the linear mixed models while specifying the binomial distribution, log link, and an autoregressive correlation structure. Through these analyses, we aim to gain insight as to specific patient factors (e.g. presenting oral health) that may modify the clinical effectiveness and safety profile associated with frequency of tooth brushing.

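### Table 2 gives no row of its own to a negative or undefined NNH, so fewer infections with more brushing falls literally in a safety-concern row; an NNH of exactly 100 is also assigned twice

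*Combined protocol and SAP*

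**What the plan says.** Section XI, Specific Aim 2, computes HAI incidence rates per person-day in each arm. It will "calculate the number needed to harm (NNH) using the single daily brushing regimen as the" reference group, with NNH21 = 1/(IR2 − IR1) and NNH31 = 1/(IR3 − IR1). Both quantities carry a sign. No formal between-group test of HAI is planned, so only the point estimate enters the decision.

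If the non-inferiority test fails, the text says: "we will define clinically-relevant “compromised” safety as an NNH of 100 per less". It explains: "This would be interpreted as 100 individuals or less being treated with the multiple daily tooth brushing" for one of them to acquire an infection that once-daily brushing would have spared.

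Table 2, presented as fixed in advance, turns this into recommendations when non-inferiority is not supported:

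- 1 versus 3, NNH 100 or more: 3 times/day, rationale "1 time/day inferior, 3 times/day safe".
- 1 versus 3, NNH below 50: 1 time/day, rationale "1 time/day inferior, but 3 times/day safety concern".
- 1 versus 3, NNH 50 to 100: go to the 1 versus 2 comparison.
- 1 versus 2, NNH 100 or more: 2 times/day, labelled safe.
- 1 versus 2, NNH below 100: 1 time/day, rationale "1 time/day inferior, but 2 times/day safety concern".

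Footnote b says the 1 versus 2 rows are "Conducted if the 1 versus 3 test of non-inferiority is not supported and" NNH31 lies between 50 and 100. Where non-inferiority is supported, NNH is marked not applicable. Nothing in the plan covers a negative or undefined NNH.

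**The concern.** A rule fixed in advance should send every possible result to exactly one row. This one does not, for three reasons.

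- **Sign.** A negative NNH is numerically below 50 and below 100. Read as written, a lower infection rate with more brushing is filed as a safety concern about more brushing.
- **Zero difference.** Equal rates make NNH undefined, and no row applies.
- **Boundary.** An NNH31 of 100 meets both the 100-or-more row and the 50-to-100 row, which lead to different actions. The text calls 100 compromised, while both 100-or-more rows call it safe.

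At stake is the only branch of the plan in which safety decides the recommended frequency. If the table is silent there, someone must choose the reading after seeing the infection counts by arm.

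**Working it through.** **1. The plan's own figures.** Per group, n = 2(z0.90 + z0.95)²/0.50² = 2(1.2816 + 1.6449)²/0.25 = 68.5, rounded up to 69. Then 3 × 69 = 207 and 207/0.60 = 345. An HAI proportion of 0.05 in 69 is 3.45 events, and the Clopper-Pearson 95% interval is 0.012 to 0.131. All of these match the Statistical Power section, and none depends on the Table 2 cut-points.

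**2. NNH values passed through the rows as written (non-inferiority not supported).**

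| NNH | 1 versus 3 | 1 versus 2 | Text |
|---|---|---|---|
| 200 | 100 or more: safe | 100 or more: safe | not compromised |
| 100 | 100 or more **and** 50 to 100 | 100 or more: safe | compromised |
| 75 | 50 to 100 | below 100: concern | compromised |
| 25 | below 50: concern | below 100: concern | compromised |
| −20, −50, −200 | below 50: concern | below 100: concern | literally 100 or less |
| undefined | none | none | none |

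**3. Examples.** With 2/69 HAIs in the 3-times arm and 5/69 in the once-daily arm, NNH31 = 1/(2/69 − 5/69) = −69/3 = −23. At an assumed 5 days per subject (345 person-days per arm), NNH31 = 1/(2/345 − 5/345) = −345/3 = −115. The size changes with the scale but the sign does not, and both values fall in the below-50 row. For the boundary, 0.06 against 0.05 gives 1/0.01 = 100. Exactly 100 cannot occur on the patient-proportion scale with 69 or 115 per arm, because 1% of these is 0.69 or 1.15 events.

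**4. How often the sign is negative.** Assumption: true HAI risk 5% in both arms (the plan's illustrative proportion).

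- Person-day scale, as in the plan's formula, simulated with an assumed 2 to 7 observed days per subject: negative about 50%; exact ties about 0.4% (69 per arm) and 0.2% (345/3 = 115 per arm).
- Patient-count scale, exact binomial: negative 0.42 and 0.44; ties 0.16 and 0.12. These ties arise from equal denominators and nearly vanish on the person-day scale.
- Range, patient-count scale, with an assumed true 3-times risk of 3% to 7% against 5%: negative 0.65 down to 0.25 (69 per arm) and 0.73 down to 0.22 (115 per arm).

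**5. The non-inferiority gate.** With 69 per group the margin is 0.50/√(2/69) = 2.937 standard errors. If plaque is truly equal, non-inferiority fails with probability 1 − Φ(2.937 − 1.282) = about 5% at one-sided 0.10 (power section), or 1 − Φ(2.937 − 1.960) = about 16% with the 95% interval (Specific Aim 1). If HAI is independent of plaque, a negative NNH reaches Table 2 in about 0.05 × 0.50 = 2.5% to 0.16 × 0.50 = 8% of trials. If once daily is worse by the full margin, failure is 90% or 97.5%, and the share is about 45% to 49%.

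**6. Scale of the cut-points.** Rates of 0.02 and 0.01 per day give NNH = 100, which is 100 person-days. At 5 days each, that is 100/5 = 20 subjects, not 100 individuals. With equal 5% risks and before any gate, a difference beyond 1/100 occurs in about 11% (69 per arm) or 6% (115 per arm) of trials per person-day. Per patient it occurs in 0.275 + 0.146 = 42% or 0.222 + 0.101 = 32%.

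**The case against.** The best defence is that the text defines NNH through infections caused by extra brushing, so only positive values can have been meant. A sensible analyst would not report a safety concern for the arm with fewer infections. That stands as evidence of intent. It does not complete the rule, because the formula is signed, the rows have no lower bound, and no sentence says what to recommend when the difference is zero or negative.

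The second defence is that the rows matter only after non-inferiority fails. That is correct, and it limits the size of the problem. A reader might infer from the sign probabilities that more than half of all trials would give a result Table 2 misreads or cannot read. The documents do not support that: NNH is not applicable when non-inferiority is supported, and the large share of ties behind such a figure belongs to patient counts, not to the plan's person-day rates.

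A reader might also infer that the trial will issue a recommendation contrary to its data. That goes too far. The documents show that the literal reading leads there, not that anyone would follow it.

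The overlap at 100 is a drafting slip with little practical weight unless NNH is rounded.

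**Conclusion.** The point holds as a defect in a prespecified decision rule. Table 2 does not handle negative or undefined NNH values, and the literal reading of a negative value contradicts the data that produced it. Once non-inferiority has failed, about half of results would be negative. That rests on equal true HAI risk of 5%, independence from plaque, and 2 to 7 observed days per subject. Across all trials the share runs from a few percent if plaque is truly equal to a little under half if once daily is worse by the full margin. The double assignment of 100, and the disagreement between text and table there, are real but rare. The sample size is unaffected. The change should be made before HAI results by arm are seen.

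**What to change.** Restate the Table 2 safety rows as intervals of the difference IRk − IR1 that are mutually exclusive and cover every value:

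- Keep zero and negative differences apart from the rows that denote harm.
- State whether the difference is risk per patient or rate per person-day, so that the 1/100 and 1/50 cut-points agree with the text's interpretation in individuals.
- Assign the boundary at 100 to one row, and make the Specific Aim 2 text, Table 2 and footnote b agree.
- Report NNH only when the difference is positive, as a back-transformed summary.

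Which recommendation attaches to each interval is for the sponsor to reconcile. The cost is one table, its footnote and a sentence or two of text, with no change to data collection or sample size.
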